6.0 Study design

Study design

Double-blinded, parallel, placebo controlled randomized 2-group complete cross-over design with 12 week washout period.

Participant Assignment

Eligible patients will be randomly assigned to two groups in 1:1 ratio.

Group A will receive 6,000 IU daily of vitamin D3 (3 capsules of 2000 IU pills).

Group B will receive an identical placebo.

[figure not shown]
Each group will be comprised of approximately 50 patients. Patients who are not able to complete the study will be replaced.

Cross-over will be done after a period of 36 weeks followed by 12 weeks washout period. After 12 week washout period, patients on either arm will be crossed over to receive the drug on the other arm (patients who were on vitamin D arm will get crossed-over to receive placebo, while patients on placebo arm will be crossed-over to receive vitamin D).

They will be stratified randomization based on the Gleason score (less than or equal to 6, OR greater than 6) as well as the season of entry (winter/spring versus summer/fall). Seasonal stratification assignment will be based on the date of randomization:

If randomized between 12/22 and 6/21, it will be considered the winter/spring group and if randomized between 6/22 and 12/21 it will be the summer/fall group.

After completion of study, patient may choose to continue vitamin D if they desire.

Duration of the trial

Patients will be followed for 36 weeks after randomization followed by a washout period of 12 weeks and then be crossed over and followed for an additional 36 weeks (total 84 weeks). 103 patients are expected to enroll over an 11 year period.

Dose Modification:

- 1). If a patient's 25(OH) D3 level reaches > 200ng/ml with 6000 IU or 3 capsules a day, or any \geq grade 3 toxicity possibly related to cholecalciferol develops, 25(OH) D3 or placebo will be discontinued for 4 weeks. Treatment will then be resumed at lower dose of 4000 IU or 2 capsules a day. If a patient misses some period of time off the study drug, the treatment will be resumed such that the patient completes a total of 36 weeks on the study drug.
- 2). If a patient's 25(OH) D3 level reaches > 200ng/ml with the lower dose modification of 4000 IU or 2 capsules a day, or any grade 3 toxicity develops, 25(OH) D3 or placebo will be discontinued for 4 weeks. Treatment will then be resumed at lower dose of 2000 IU or 1 capsule a day.

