Prior studies have used similar design and there are substantial data that indicate that 36 weeks is a time period over which modification of PSA slope can be assessed.^{65, 66} In extensive vitamin D literature there are substantial data to indicate that "equilibrium" is achieved in 25(OH)D3 levels after a 12 weeks equilibration period. The literature indicates that 3 months is adequate "washout" to re-establish serum levels.^{60, 61} The half-life of 25(OH)D3 in the circulation is reported as \approx 1 mo in humans, the results for the submariners suggest a 2-mo half-life.^{67, 68} Conventional pharmacology indicates it should take 4 half-lives before a drug's equilibrium is achieved. Unlike a conventional drug, 25(OH)D3 is a metabolite whose concentration can be altered through balance between its production and clearance so that an equilibrium can be achieved earlier than would be expected from the half-life.^{69,70}

Monitoring

Parameters noted in the above table will be assessed as per standard clinical laboratory procedures. 25(OH) D3 levels will be measured in the hospital chemistry laboratory and are the standard measure for determination of vitamin D health. PTH levels after basal level will be measured as a research test in the lab of [name].

Procedure for collecting serum samples for PTH measurements.

Collect 5 mL blood in a red top tube (no additives). It is recommended that all samples to be collected A.M (to avoid diurnal variation issues). Blood samples are spun in a refrigerated centrifuge at 2000 x g for 10 min. Divide serum into two aliquots of 1.0 mL each/ patient (this avoids repetitive freezing and thawing every time the assay is performed). Freeze immediately at -70°C in plastic tubes. Under these storage conditions PTH is stable for up to 11 months.

Please call [name] to notify [name] lab of impending sample or if there are questions.

In addition all patients will be offered to enroll, after informed consent, on the DBBR-vitamin D repository trial.

PSA Measurement

Once enrolled on study, individual patients should get their PSA drawn at the same laboratory to ensure correct calculation of PSA dynamics for that individual.

Correlative/Special Studies

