10.7 Data Safety and Monitoring

If any literature becomes available which suggests that conducting this trial is no longer ethical, the study will be terminated and the IRB will be notified of the new findings. The IRB will be notified of any change in the risk/benefit ratio that would affect whether the study should continue. All serious adverse events will be reported to the IRB according to the established guidelines. A cumulative summary of all adverse events occurring on this study will also be submitted to the IRB at six months review. Toxicity is reported, as required, to the FDA. All study data reviewed and discussed during these meetings will be kept confidential. Any breech in participant confidentiality will be reported to the IRB.

11. Statistical Analysis

Power analysis:

A 2x2 cross-over design with total sample size 100 achieves approximately 80% power to detect 0.5 effect size (the relative magnitude of the effect under the alternative) at significance level 0.05. In other words, assuming the $\text{Log}_2(\text{PSA})$ slope prior to therapy is 0.7 ng/ml/yr. with a standard deviation as 0.7 (based on statistical evaluation of data provided by [name] from his trial of cholecalciferol replacement in men with PSA rising after local therapy.⁵⁵, this design is able detect a 50% reduction of PSA doubling time.⁷¹

Statistical analysis plan:

This is 2 by 2 cross over trial. To address the research objectives, we want to pool information across periods by taking account of the correlation among repeated responses for each individual. The $\text{Log}_2(\text{PSA})$ will be analyzed by linear mixed model in which the fixed effects include treatment (1 for vitamin D3, 2 for control), period (0 for pre study, 1 for first 36 weeks and 2 for second 36 weeks), time (as a continuous variable), time and period interaction, and a variable indicating carry-over effect (1 if the previous treatment assignment is vitamin D3, 2 if the previous treatment assignment is control). The random effect includes random intercept and slope (and a quadratic term if necessary). The significance in the difference between PSA responses for vitamin D3 group and control groups will be assessed by approximate t tests. This will be done using SAS PROC MIXED (SAS 9.1.3., SAS Institute Inc., Cary, NC, USA). The pattern of response of PSA dynamics as well as the absolute change in PSA following vitamin D3 supplementation will be analyzed similarly using the mixed model approach.

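### As specified, the carry-over term takes up the whole period-2 level contrast, so the second period barely informs the vitamin D3 effect; the primary contrast should be on the log2(PSA) slope

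*Combined protocol and SAP*

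**What the plan says.** Section 6.0 (Study design) sets two sequences of 36 weeks, 12 weeks of washout and 36 weeks on the other arm: "patients who were on vitamin D arm will get crossed-over to receive placebo", and the placebo men move the other way.

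Section 11 (Statistical analysis plan) gives the aim of the primary model: "we want to pool information across periods by taking account of the correlation among repeated responses for each individual". Its fixed effects are treatment, period (0, 1, 2), continuous time, time by period, and "a variable indicating carry-over effect (1 if the previous treatment assignment is vitamin D3, 2 if the previous treatment assignment is control". The random effects are intercept and slope, with a quadratic if needed. The difference between arms "will be assessed by approximate t tests". There is no treatment-by-time term and no rule for dropping the carry-over term. Secondary objective 1 is to use the same mixed-model approach.

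The power statement in section 11 is on the log2(PSA) slope, 0.7 per year "with a standard deviation as 0.7": "A 2x2 cross-over design with total sample size 100 achieves approximately 80% power to detect 0.5 effect size" "at significance level 0.05".

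Two other places matter. The PSA velocity (PSAV) analysis in section 11 compares each man's period 1 minus period 2 difference between sequences, with no carry-over term. Section 6.1 discusses the washout: "Conventional pharmacology indicates it should take 4 half-lives", but it then argues that 25(OH)D3 can equilibrate sooner and that 3 months is enough.

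**The concern.** Two sequences and two treated periods give only two contrasts between sequences. If treatment and carry-over are both free level effects, period 1 estimates treatment and period 2 is used up in estimating carry-over. Each man's PSAs in weeks 48 to 84 then add almost nothing to the primary estimate, which defeats the stated purpose of pooling. Secondary objective 1 inherits the problem.

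Two further gaps affect the same model. The 1/2 coding has no value for pre-study and first-period rows, so a programming choice decides whether the effect can be estimated. And the model tests a level shift, whereas the trial is powered on a change in slope.

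**Working it through.** **Inputs from the documents.** About 50 men per sequence, 1:1 (section 6.0). PSA at weeks 12, 24 and 36 of each period (section 6.1), which puts period 2 at weeks 60, 72 and 84. Slope SD 0.7, effect size 0.5 and alpha 0.05 (section 11), so the slope difference is 0.5 x 0.7 = 0.35 per year.

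**Assumed, because the documents do not give them.** Five PSAs over the 2 years up to and including baseline; random-intercept SD 1; random-slope SD 0.35 to 0.7, one slope per man; residual SD 0.2 to 0.3 log2 units; rows without a previous treatment coded as control or none.

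1. **The stated power.** Two groups of 50 with one value each: SE = SD x sqrt(2/50) = 0.2 SD and 0.5/0.2 = 2.5, giving 80.4% power one-sided and 70.5% two-sided. A cross-over of 100 men: SE = SD x sqrt(2(1 - rho)/100), which at rho = 0 gives 94.2% two-sided. A cross-over of 50 men (100 patient-periods) at rho = 0.2 gives 79.8% two-sided. The stated 80% therefore reproduces as a one-sided 50 v 50 comparison or as a 50-man cross-over, but not as a 100-man cross-over. Sidedness is not stated.

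2. **Aliasing.** Let T be the treatment effect and C the carry-over effect. The sequence difference (vitamin D3 first minus placebo first) is T in period 1 and C - T in period 2. With both free, the estimate of T is the period-1 difference. With one value per period its variance is 2/50 = 0.040 SD² at every within-man correlation from 0 to 0.9. Without C it is 2(1 - rho)/100: 0.020 at rho 0 and 0.010 at rho 0.5.

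3. **The mixed model as written.** Generalised least squares gives these SEs for the treatment level effect:

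| Slope SD, residual SD | Carry-over fitted, all data | Period 2 deleted | No carry-over term |
|---|---|---|---|
| 0.35, 0.2 | 0.0441 | 0.0446 | 0.0171 |
| 0.7, 0.3 | 0.0665 | 0.0672 | 0.0257 |

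Period 2 improves the SE by about 1% (for example 1 - 0.0665/0.0672 = 1.0%). Over a wider grid of assumed variances and numbers of pre-study PSAs the gain is 0.1% to 4.7% without a random quadratic, and at most 16% with one.

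4. **Coding left missing.** PROC MIXED drops the pre-study and period-1 rows. Among the period-2 rows, treatment and carry-over are complements, and the fixed-effect matrix has rank 3 for 4 columns.

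5. **Deleting the term.** Suppose vitamin D3 changes the slope by -0.35 per year and the growth prevented is not regained in washout. The period-1 level effect over weeks 12, 24 and 36 averages -0.35 x 24/52 = -0.16. At the start of period 2 the vitamin-D3-first men are still 0.35 x 36/52 = 0.24 lower, so the period-2 sequence difference is -0.24 + 0.16 = -0.08. The simple cross-over estimate is half of [-0.16 - (-0.08)], or -0.04. The mixed model, which also weights pre-study PSAs, gives about -0.063. Effect over SE for the two rows above is 0.1615/0.0441 = 3.66 and 0.1615/0.0665 = 2.43 with the term, and 0.063/0.0171 = 3.68 and 0.063/0.0257 = 2.45 without it. Over all four combinations of slope SD and residual SD, two-sided power is 94-95% with the term and about 96% without at residual SD 0.2, and 67-72% and 67-70% at 0.3.

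6. **Slope contrast within period.** With a separate intercept per man and period, the slope from three PSAs has error SD = residual SD / sqrt(2 x (12/52)²) = residual SD / 0.326, that is 0.613 or 0.919. The man's own slope cancels in period 1 minus period 2. The treatment SE is half of sqrt(2 x SD² x (1/50 + 1/50)) = 0.141 x SD, or 0.087 and 0.130. Then 0.35/0.087 gives about 98% power and 0.35/0.130 about 77%. A period-1-only slope contrast that also uses pre-study PSAs has SE 0.125 and 0.187. A level-only carry-over term leaves 0.130 unchanged; a carry-over term on the slope returns it to 0.187.

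7. **Residual 25(OH)D3.** Twelve weeks is about 2.76 half-lives at 1 month and 1.38 at 2 months (section 6.1), so 2^-2.76 = 15% to 2^-1.38 = 38% of the increment remains at week 48.

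**The case against.** The strongest reply is that the carry-over term costs the planned level test almost no power and guards against a real bias, because washout does not reverse PSA growth already prevented. Step 5 bears this out, so the remedy cannot be simply to strike the term.

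A reader might infer that the term costs the trial the gap between 70% and 94% power. The documents do not support that. Those figures come from one slope value per man and period; the section 11 model tests a level and also uses pre-study PSAs. The gain from the slope contrast is a few points up to about ten.

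A reader might also infer that crossing men over adds almost nothing to the trial. That is too strong: the PSAV t test already uses both periods without a carry-over term and is unaffected. It is supplementary, however, is on PSAV rather than log2 slope, and appears limited to men with three or more earlier PSAs from the same laboratory.

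Finally, the coding is unstated, and some readings break the aliasing: a sequence indicator on all rows, or an off-drug week-48 PSA placed in period 2. The plan specifies neither, and the section 6.1 table has no week-48 column. This limits certainty about what would be programmed; it does not make the model adequate.

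**Conclusion.** The point holds for the primary mixed model and the analyses modelled on it. With rows lacking a previous treatment coded as control or none, the level contrast is identified by period 1 together with pre-study PSAs, and the aliasing itself is algebra that needs no assumed variance. The 1% figure and its range, the shrinkage from -0.16 to -0.06 and the power comparisons rest on the assumed variances and PSA times, and the shrinkage also on a slope effect that persists through washout. The pre-study PSAs do sharpen the estimate, but that gain does not come from crossing over.

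The underlying mismatch is that treatment enters as a level shift while the trial is powered on slope. Putting the contrast on slope brings period 2 into the estimate. Against a period-1-only slope contrast, the SE falls from about 0.125 to 0.087 at residual SD 0.2 and from 0.187 to 0.130 at 0.3. The model should be changed before the data are analysed.

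**What to change.** Make the primary contrast the treatment effect on log2(PSA) slope within period, in all randomised men. Either fit treatment by time since the start of the period with period-specific intercepts, or compare each man's period 1 minus period 2 slope between sequences, as section 11 already does for PSAV.

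Leave carry-over on the slope out of the primary model. Report a carry-over estimate with its confidence interval, and the period-1-only estimate, as sensitivity analyses. A level-only carry-over term may stay. Define the treatment and carry-over codes for pre-study and first-period rows, state the period to which any week-48 PSA belongs, and state whether the test is one- or two-sided. Apply the same specification to secondary objective 1.

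The cost is SAP wording; the contrast can be fitted with the three scheduled PSAs per period. The downside is some attenuation if residual 25(OH)D3 acts into period 2. If the effect were proportional to the level, it would be about 1-9% relative to a period-1-only slope, but that proportionality, and the four PSAs per period used for that figure, are assumptions that the documents do not establish.
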